Study Protocol

TRANSFORM Heart Failure with Reduced Ejection Fraction: TRANSFORM-HFrEF (Version 1.1)

A Randomized Registry Trial to Evaluate Best Practices and Improve Adherence to Guideline Directed Medical Therapy for Heart Failure with Reduced Ejection Fraction

[name], MD FACC, FESC

Trustee, American College of Cardiology, Washington, DC

Cardiology Division, Massachusetts General Hospital

Hutter Family Professor of Medicine, Harvard Medical School

Senior Cardiometabolic Faculty, Baim Institute for Clinical Research

Boston, MA

Correspondence:

[name] MD, FACC, FESC Massachusetts General Hospital [name] P: [contact]

F: [contact] F: [contact]

E: [contact]

T: [name]

A. Study Overview

1. Purpose of the Study

The goal of the TRANSFORM-HFrEF trial will be to study the current guideline directed medical therapy (GDMT) landscape for HFrEF, and determine effective methods and models of increasing adherence to GDMT and improving Quality of Life (QOL) in outpatient settings within the context of the 20-minute visit. This will be achieved through a randomized evaluation that shifts standard clinical interview and documentation requirements outside the office visit and building the patient and physician relationship through trust and shared goal setting.

2. Background and Significance

Heart Failure (HF) is the cardiovascular epidemic of the 21st century, affecting millions of patients world-wide. It is believed that HF is the only cardiovascular diagnosis rising in incidence among elderly patients and is the #1 diagnosis leading to hospitalization among Medicare recipients. In addition to being increasingly prevalent, HF has a poor outlook after initial diagnosis and is associated with poor quality of life (QOL) in affected patients; this not only leads to burden on patients, family and other caregivers, but also on the healthcare system. For all these reasons, optimizing the understanding and care of patients with HF is a major priority.

Although clinical practice guidelines clearly articulate optimal GDMT for care of patients with HFrEF, implementation of GDMT into the management of such patients has proven to be suboptimal, with most patients under-treated relative to goal therapy.

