The PINNACLE Registry® is the largest outpatient cardiovascular clinical data registry in the world, with millions of patients drawn from thousands of sites around the US representing over 10,000 outpatient providers. The registry has a comprehensive goal of improved patient care. In addition to using the PINNACLE Registry®, non-PINNACLE sites within large health systems will be recruited and randomized into the intervention and usual care arms respectively.

[figure not shown]
The Specific Aims of this study will be:

- To evaluate ability of ACC Solution Sets and Patient Resources to improve initiation and titration
 of GDMT for eligible patients with HFrEF Left Ventricle Ejection Fraction (LVEF) ≤ 40%.
- To evaluate change in QOL between patients in the Intervention arm and the Usual Care arm.
- Examine relative change in GDMT among higher risk versus lower risk patients in the Intervention arm and Usual Care arm.

In this randomized registry trial, sites will be invited to participate in a 6-month study aimed at various processes of care in HFrEF. Sites would be informed that they might be asked to participate in an intensive intervention to improve GDMT prescription or in a study of QOL in HFrEF. Once a list of sites interested in participating is created, sites would be randomized into two arms: an intervention group and a usual care group.

AMERICAN

(**Figure 1**): This graphic shows both usual care and intervention arm tracts.

Study Population:

- Patients from practices participating in the PINNACLE Registry® (these include those that are
 part of integrated health systems, stand-alone, and other practice environments); as well as
 patients from other practices (these include those that are part of integrated health systems,
 stand-alone, and other practice environments) with pre-existing data interfaces with study
 partner HealthReveal.
- Patient cohorts will have the following **inclusion** criteria:
 - Age ≥18 years
 - Clinical diagnosis of HF with EF ≤40% documented within 1 year of enrollment
 - Receiving ≥1 oral medication for HF at study enrollment (including diuretics, ACEI/ARB/ARNI, beta-blockers, MRA, SGLT2i or thiazide diuretics.
- Patient cohorts will have the following **exclusion** criteria:
 - Current or anticipated participation in a clinical trial
 - Currently receiving comfort care or enrolled in hospice
 - Life expectancy <1 year
 - o History of or plan for heart transplantation or left ventricular assist device

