- Quick Tips series provides guidance on many of the topics that are raised during medical visits, but we may not have sufficient time to go into great detail about; for example, how to record daily weights, stay active, limit sodium, take medications, watch for triggers that can exacerbate heart failure, and pay attention to emotional health and mental outlook

The Usual Care arm, will be managed as close to "true" usual care as possible. To avoid influencing management, once randomized to usual care, other than to collect QOL measures (assessed using the Kansas City Cardiomyopathy Questionnaire-23) at baseline, 3 months, and 6 months, study sites will not be contacted until the study has completed and they will be unaware of allocation to usual care. They will not receive specific pre-visit guidance, and though publicly available, sites will not be specifically provided ACC tools.

B. Data Management

Participating sites submit data using an electronic health record (EHR) system integration (SI) tool, where relevant registry data fields can be extracted from a practice's EHR and is then transmitted to a secure database.

Intervention Arm

Steps include:

Data extraction: Mapped to pre-specified data fields, a data extractor (such as that provided by FIGmd) will extract the EHR data to storage at Veradigm for PINNACLE sites. FigMD has historically provided the data extractor solution for the PINNACLE Registry and provides similar services to multiple medical societies across the United States of America. Data extracted may include the following: age, sex, LVEF, medication list (including doses), and laboratory results (such as basic metabolic panel). For the purposes of the study, data from the local EHR will be extracted on a weekly basis.

Creation of Reveals: Following, a similar extractor will then process data to HealthReveal for non-PINNACLE sites, where a dashboard will be created. This dashboard will include a) lists of eligible patients for the study and b) an update on opportunities for further medication optimization. The latter information will be based on guideline-directed medical targets as articulated in the ACC 2020 Expert Consensus Decision Pathway document on management of HFrEF. The dashboard containing the reveals will be conveyed to the sites.

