The recommended adjustment(s) will be conveyed using proprietary software from HealthReveal, with a suggested follow up plan. All reminders regarding dosing targets are based on the 2020 ACC Expert Consensus Decision Pathway for Optimization of Heart Failure Treatment.

Additionally, during visits at baseline, 3 months, and 6 months, the KCCQ-23 will be completed.

In the Usual Care arm, during visits at baseline, 3 months, and 6 months, the KCCQ-23 will be completed.

9. Risk/Benefit Assessment

As study procedures reflect optimized heart failure care via guideline recommendations supported by the clinical judgment of the managing physician, there is no envisioned procedural risk to patients through involvement in the study. No testing, time, risk, or procedures beyond those required for routine care will be imposed. The primary risk associated with this project is the potential for a breach of patient confidentiality. The ACCF has established a robust plan for ensuring appropriate and commercially reasonable physical, technical, and administrative safeguards are in place to mitigate such risks as described in the Data Management section of this protocol.

10. Costs to the Subject and Compensation

There are no costs or compensation to the patient for participation in the TRANSFORM-HFrEF study.

11. Data Analysis and Statistical Considerations

Primary endpoint; compared to usual care:

From baseline to 6 months change in average composite endpoint of target dose achievement for the main classes of drugs (RASi/beta blockers/MRA/SGLT2i) among eligible patients without documented contraindications or intolerance.

Goal doses will be based on the 2020 ACC Expert Consensus Decision Pathway for Optimization of Heart Failure Treatment (4).

To calculate this composite:

Numerator = receiving ARNI/ACEI/ARB at 50% or higher of target dose + receiving evidence-based beta blocker at 50% or higher of target dose + receiving MRA at 50% or higher of target dose + receiving SGLT2i at 50% or higher of target dose.

Denominator = eligible to receive ARNI/ACEI/ARB and no documented reason for not receiving higher dose, eligible to receive evidence-based beta blocker and no documented reason for not receiving higher dose, and eligible to receive MRA and no documented reason for not receiving higher dose, and eligible to receive SGLT2i and no documented reason for not receiving higher dose.

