- 8) Change in % eligible taking MRA during course of the study.
- 9) Change in % eligible taking SGLT2i during course of the study.
- 10) Relative improvement in GDMT composite score among subgroups of interest. This may include pre-specified analyses among patients the following characteristics:
 - a. Elderly patients (age ≥ 75 years)
 - b. New onset HF
 - c. Recently hospitalized patients
 - d. Those with LVEF <25%
 - e. Those with estimated glomerular filtration rate <30 mL/min/1.73m²
 - f. Baseline systolic blood pressure <100 mm/Hg
 - g. Absence of RASi at baseline
 - h. Absence of beta blocker at baseline
 - Patients with high baseline total medication burden (5 or more meds for all conditions)
 - j. Academic versus Private practice

Power calculations: The primary endpoint will compare central tendency in score changes between the two groups (6-month score - baseline score; this gives a range of score changes from -3 to +3). We will assume a 5% rate of score decreases, with rates for -3, -2 and -1 assumed equal between the two groups. To compare such changes a two-sided Wilcoxon ranksum test at a 0.05 significance level with 90% power will be employed. Assuming 5% of usual

care patients have an increase in score versus 10% of the intervention arm change by 1 point, a sample size of 2560 (1280 per arm) would be needed. Assuming a reasonable 20% loss to follow-up and/or missingness in this registry analysis, this makes a total of 3072 (1536 per arm). This not only provides power for the primary endpoint, but also for the secondary and exploratory endpoints, including change in QOL metrics.

12. Data and Safety Monitoring

This is an observational study comparing the effectiveness of two standards of care based on secondary use of data collected in the conduct of care and patient reported outcomes. The purpose of this study is not to gather data with regards to the safety profile and/or effectiveness of specific drugs. This study does not proscribe which treatment patients will receive. There is no Data Safety Monitoring Board for this study.

Adverse events (should they occur) will be captured at the clinical site level. Patients reporting adverse events will address these with their providing physician.

13. Data Storage and Confidentiality

Please refer to the Data Management section for details regarding how data captured in this study is stored and how the confidentiality of such data is maintained.

References

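### Section 12 calls a site-randomised trial observational and plans no comparison of harms by arm, and the primary composite, with no fixed time for judging eligibility, may miss down-titration due to intolerance

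*Protocol*

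**What the plan says.** **Design.** Section 12 (Data and Safety Monitoring) states: "This is an observational study comparing the effectiveness of two standards of care". The title reads "A Randomized Registry Trial to Evaluate Best Practices", and Section 3 says that "sites would be randomized into two arms: an intervention group and a usual care group". Under Section 8, only intervention sites receive a pre-visit assessment with recommended changes to heart failure drugs.

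**Harms.** Section 12 says that safety data on specific drugs are not the study's purpose, that there is no monitoring board, and that "Adverse events (should they occur) will be captured at the clinical site level". None of the primary, secondary or exploratory endpoints in Section 11 is a harm.

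**Primary endpoint.** Section 11 divides the number of classes at 50% or more of target dose by the number of classes for which the patient qualifies. Each class enters the denominator under a condition of the same form. For the MRA it is "eligible to receive MRA and no documented reason for not receiving higher dose". No time point is given for judging this. The same section presents it as an advantage that the composite reflects down-titration as well as up-titration.

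**Data at hand.** In both arms, the Data Management section says the extract may include medication lists with doses and laboratory results, with the basic metabolic panel as the example.

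**The concern.** Two matters meet here. First, the label in Section 12 does not fit the design. Sites are assigned at random to an intervention meant to change prescribing, so a difference between arms in tolerability is a possible effect of the intervention. The protocol plans no result that would show it.

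Second, the denominator condition can depend on what happens after randomisation. If titration leads to an intolerance and the site documents it, the class may leave the denominator instead of counting as not achieved. The composite could then be flat or higher in a patient whose treatment was cut back. Only intervention sites are prompted to titrate, and usual-care sites are not to know that medical management is being monitored, so documentation of intolerance may differ by arm.

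At stake is how a favourable primary result would be read. The exploratory subgroups include patients aged 75 or over, with eGFR below 30, or with systolic pressure below 100. A gain in the composite there would stand without a matching result on potassium, renal function or drug withdrawal.

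**Working it through.** **Step 1. Reproduce the protocol's own figures.** Score = classes at 50% or more of target / classes eligible with no documented reason. Change = 6-month score minus baseline score. The three worked examples in Section 11 give:
- 1/3 to 3/3: +0.667 (protocol 66.7%)
- 0/2 to 1/2: +0.500 (protocol 50.0%)
- 0/3 to 1/3: +0.333 (protocol 33.0%, a rounding difference)

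The ratio reading is therefore the one the examples use. In the second example the MRA is absent from the denominator because of earlier hyperkalaemia. It is absent at both times, so no example shows a class becoming ineligible during the study.

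**Step 2. Apply the formula to an intolerance first documented during follow-up.** The text permits three treatments of the denominator.

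| Event | Fixed at baseline | Re-judged at 6 months | Removed at both times |
|---|---|---|---|
| 3 classes, 1 at goal; a below-goal class is dropped | 1/3 to 1/3 = 0 | 1/3 to 1/2 = +0.17 | 1/2 to 1/2 = 0 |
| 3 classes, 2 at goal; the below-goal class is dropped | 2/3 to 2/3 = 0 | 2/3 to 2/2 = +0.33 | 2/2 to 2/2 = 0 |
| 4 classes, 3 at goal; the below-goal class is dropped | 3/4 to 3/4 = 0 | 3/4 to 3/3 = +0.25 | 3/3 to 3/3 = 0 |
| 3 classes, 3 at goal; one of these is lost | 3/3 to 2/3 = -0.33 | 3/3 to 2/2 = 0 | 2/2 to 2/2 = 0 |
| 3 classes, 2 at goal; one of these is lost | 2/3 to 1/3 = -0.33 | 2/3 to 1/2 = -0.17 | 1/2 to 1/2 = 0 |
| 4 classes, 4 at goal; one of these is lost | 4/4 to 3/4 = -0.25 | 4/4 to 3/3 = 0 | 3/3 to 3/3 = 0 |

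**Step 3. Read the table.**
- A spurious gain arises only in the re-judged column, and only when the dropped class was below goal and at least one other class was at goal. With a baseline score of 0, dropping a class leaves it at 0.
- A hidden or reduced loss arises in both right-hand columns. One exception is the loss of a patient's only at-goal class with re-judging: 1/3 to 0/2 = -0.33, the full fall.
- Removal at both times also enlarges gains elsewhere. One class reaching goal while another is removed scores 0/2 to 1/2 = +0.50, instead of 0/3 to 1/3 = +0.33.

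**Step 4. What a by-arm harms table could resolve.** With 1280 analysed per arm (Section 11) and a common event rate p, the 95% half-width of the difference is 1.96 x sqrt(2p(1-p)/1280). The protocol gives no event rate, so p is assumed:
- p = 3%: 1.3 percentage points
- p = 5%: 1.7 points
- p = 8%: 2.1 points

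These assume a result for every patient and ignore clustering by site. The real intervals would be wider.

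**The case against.** **Timing may be settled elsewhere.** The protocol does not say that eligibility is judged again at 6 months, all three examples keep one denominator, and an SAP that is not shown may fix the rule. This stands, and it makes the spurious gain conditional. It does not rescue the statement about down-titration, because removing the class at both times also hides the loss.

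**Excluding documented intolerance is reasonable.** A site should not be marked down for respecting a contraindication. That holds for one known at baseline. An intolerance that arises after randomisation may itself result from the intervention.

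**The scale is not settled.** The power paragraph in Section 11 describes changes from -3 to +3, which suggests a count of classes. On a count, dropping a below-goal class changes nothing and losing an at-goal class scores -1. The figures above hold on the ratio scale of the worked examples.

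**Other endpoints exist.** A reader might infer that no other result would show the loss. The protocol does not support that. The two secondary endpoints, on achieved doses and on target-dose achievement by class, carry no stated eligibility restriction and could show a net fall. They would not show its cause.

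**Section 9 gives its own rationale.** It relies on guideline-based care under the managing physician's judgement, with nothing beyond routine procedures. A reader might infer that the observational label is why harms are not assembled. Section 12 sets the two side by side without saying so.

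**Laboratory data may be thin.** The extract only may include them, and usual-care follow-up is at the site's discretion. This limits how complete a harms summary would be.

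**Conclusion.** The point holds in conditional form. Two parts need no assumption: the description in Section 12 contradicts the randomised design, and the protocol plans no comparison of harms by arm. The third part is that the composite may not capture down-titration due to intolerance. Per patient, an at-goal class lost can score 0 instead of -0.33 or -0.25. If eligibility is re-judged, a below-goal class dropped can score up to +0.33 with three eligible classes, or +0.25 with four, with no gain in treatment.

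These figures rest on the ratio scale and on eligibility not being fixed at baseline. A reader might infer that the primary result will credit harm as improvement, or that every harm-related down-titration escapes it. The protocol supports neither: the gain needs re-judging and a dropped class below 50% of target, and in some cases a loss still shows in part or in full. The size and direction of any bias between arms cannot be computed, because no rate of intolerance or of its documentation is given. The correction should be made because it is cheap and bears on what a positive result would mean. It does not call the randomised comparison itself into question.

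**What to change.** 1. In Section 12, describe the study as a site-randomised trial of a decision-support intervention.
2. In Section 11, fix each patient's eligible classes at baseline for the primary composite, so that a class stopped for intolerance arising during the study counts as not achieved. Report the version re-judged at 6 months as a sensitivity analysis.
3. Pre-specify a by-arm summary, from extracted data where available, of potassium, creatinine/eGFR, and dose reductions or stops with documented intolerance by class. Give it per patient and per test, with intervals that allow for site clustering, beside the primary result.

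Step 3 alone would leave the artefact in the primary result, so step 2 is needed too. None of this sets a dose or a clinical rule.

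The cost is a wording change, an endpoint clarification and a few extra tables. There are two downsides: intervention patients may be tested more often, which is why both denominators are needed, and laboratory data may be incomplete, so their availability should be confirmed and missingness shown by arm.

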APPENDIX A: CardioSmart materials

Heart Failure Action Plan	Workbook- Managing My Heart Failure at Home Tab
Heart Failure: Making the Most of	Worksheet/Addendum to Action Plan Workbook- Managing my
My Follow Up Visit	Heart Failure at Home Tab
My Daily Heart Failure Tracker	Worksheet- Managing my Heart Failure at Home Tab
My Heart Failure Checklist	Checklist- Managing My Heart Failure at Home Tab
Heart Failure: Caregivers	Fact Sheet Resource Tab
Heart Failure: FAQs	Fact Sheet Resource Tab

Heart Failure: Questions to Ask	Fact Sheet Resource Tab
Heart Failure, The Basics	Fact Sheet Resource Tab
Quick Tips: Heart Failure	Quick Tips Resource Tab
Quick Tips Sheet: Daily Weight Check	Quick Tips Resource Tab
Quick Tips Sheet: Minding Your	Quick Tips Resource Tab
Emotional Health	
Quick Tips: Exercise and Your Heart	Quick Tips Resource Tab
Quick Tips: Heart Failure	Quick Tips Resource Tab
Medications	
Quick Tips: Limiting Salt	Quick Tips Resource Tab
Quick Tips: Heart Failure Signs and	Quick Tips Resource Tab
Symptoms	
Quick Tips: Triggers and What To Do	Quick Tips Resource Tab
